5.7.1. Deviations Assessed Prior to Randomization

At Screening, the investigator will assess participants against the inclusion and exclusion criteria as set out in the protocol.

5.7.2. Deviations Assessed Post-Randomization

A full list of protocol deviations for the study report will be compiled prior to database closure. Any significant deviation from the protocol will be reviewed prior to database closure and a decision taken regarding evaluation for each analysis population.

6. ENDPOINTS AND COVARIATES

6.1. Efficacy Endpoint(s)

None.

6.2. Safety Endpoints

An adverse event is considered a Treatment-Emergent Adverse Event (TEAE) if the event started during the effective duration of treatment. All events that start on or after the first administrated day and time/start time, if collected, but before the last dose plus the lag time will be flagged as TEAEs. The algorithm will not consider any events that started prior to the first dose date.

The following data are considered in standard safety summaries (see protocol for collection days and list of parameters):

- adverse events,
- laboratory data.

6.3. Other Endpoints

6.3.1. PK Endpoints

Blood samples for PK analysis of prazosin will be taken according to the Schedule of Activities given in the protocol.

Page 9 of 17

The following PK parameters will be calculated for prazosin (if possible) from the concentration-time data using standard noncompartmental methods:

PK Parameter	Analysis Scale	Prazosin
AUC_{inf}^{*}	ln	A, D
AUC _{last}	ln	A, D
C _{max}	ln	A, D
T _{max}	R	D
t _{1/2} *	R	D

Table 3. Noncompartmental PK Parameters

Key: A=analyzed using statistical model, D=displayed with descriptive statistics, ln=natural-log transformed, R=raw (untransformed), *=if data permits.

6.3.2. PD Endpoints

None.

6.4. Covariates

None.

7. HANDLING OF MISSING VALUES

For the analysis of safety endpoints, the sponsor data standard rules for imputation will be applied.

7.1. Concentrations Below the Limit of Quantification

In all data presentations (except listings), concentrations below the limit of quantification (BLQ) will be set to zero. (In listings BLQ values will be reported as "<LLQ", where LLQ will be replaced with the value for the lower limit of quantification).

7.2. Deviations, Missing Concentrations and Anomalous Values

In summary tables and plots of median profiles, statistics will be calculated having set concentrations to missing if 1 of the following cases is true:

- 1. A concentration has been collected as ND (ie, not done) or NS (ie, no sample).
- 2. A deviation in sampling time is of sufficient concern or a concentration has been flagged anomalous by the pharmacokineticist.

Note that summary statistics will not be presented at a particular time point if more than 50% of the data are missing.

7.3. Pharmacokinetic Parameters

Actual PK sampling times will be used in the derivation of PK parameters.

If a PK parameter cannot be derived from a participant's concentration data, the parameter will be coded as NC (ie, not calculated). Note that NC values will not be generated beyond the day that a participant discontinues.

In summary tables, statistics will be calculated by setting NC values to missing; and statistics will be presented for a particular treatment with \geq 3 evaluable measurements. For statistical analyses (ie, analysis of variance), PK parameters coded as NC will also be set to missing; and analyses will not be performed for a particular parameter if more than 50% of the data are NC.

If an individual participant has a known biased estimate of a PK parameter (for example due to an unexpected event that might occur before all the compound is adequately absorbed in the body), this will be footnoted in summary tables and will not be included in the calculation of summary statistics or statistical analyses.

If an individual participant has a predose concentration ≤ 5 percent of the C_{max} value, then that participant's data can be included in all pharmacokinetic measurements and calculations without any adjustments. If the predose value is >5 percent of C_{max} , the PK parameters for that period will be excluded for that participant from all bioequivalence evaluations.

8. STATISTICAL METHODOLOGY AND STATISTICAL ANALYSES

8.1. Statistical Methods

Bioequivalence of PK parameters will be determined by constructing 90% confidence intervals around the estimated difference between the Test and Reference treatments using a mixed effects model based on natural log transformed data. The mixed effects model will be implemented using SAS Proc Mixed, with REML estimation method and Kenward-Roger degrees of freedom algorithm.

8.2. Statistical Analyses

Pharmacokinetic and statistical analysis will be performed for prazosin. Data from the 2 Cohorts will be analyzed separately.

Cohort 1:

Natural log transformed PK parameters (AUC_{inf} (if data permit), AUC_{last} , and C_{max}) will be analyzed using a mixed effect model with sequence, period and treatment as fixed effects and participant within sequence as a random effect. Estimates of the adjusted mean differences (Test-Reference) and the corresponding 90% confidence intervals will be obtained from the model. The adjusted mean differences and the 90% confidence intervals for the differences will be exponentiated to provide estimates of the ratio of adjusted geometric means (Test/Reference) and the 90% confidence intervals for the ratios.

Page 11 of 17

For primary objective, bioequivalence of the Test treatments (Treatment B and Treatment C) relative to Reference treatment (Treatment A) will be concluded if the 90% confidence intervals for the ratio of adjusted geometric means of Test treatments (Treatment B and Treatment C) relative to Reference treatment (Treatment A) for AUC_{last} and C_{max} fall wholly within (80%, 125%).

Cohort 2:

Natural log transformed PK parameters (AUC_{inf} (if data permit), AUC_{last} , and C_{max}) will be analyzed using a mixed effect model with sequence, period and treatment as fixed effects and participant within sequence as a random effect. Estimates of the adjusted mean differences (Test-Reference) and the corresponding 90% confidence intervals will be obtained from the model. The adjusted mean differences and the 90% confidence intervals for the differences will be exponentiated to provide estimates of the ratio of adjusted geometric means (Test/Reference) and the 90% confidence intervals for the ratios.

For primary objective, bioequivalence of the Test treatment (Treatment E) relative to Reference treatment (Treatment D) will be concluded if the 90% confidence intervals (CI) for the ratio of adjusted geometric means of Treatment E (5 mg capsule, Ascoli) relative to Treatment D (5 mg capsule, Barceloneta) for AUC_{last} and C_{max} , fall wholly within (80%, 125%).

Residuals from the model will be examined for normality and the presence of outliers via visual inspection of plots of residuals vs predicted values and normal probability plots of residuals but these will not be included in the clinical study report. If there are major deviations from normality or outliers then the effect of these on the conclusions will be investigated through alternative transformations and/or analyses excluding outliers. Justification for any alternative to the planned analysis will be given in the report of the study.

The PK parameters AUC_{last} , AUC_{inf} , C_{max} , T_{max} , and $t_{\frac{d}{2}}$ will be summarized descriptively by treatment.

Parameter	Summary Statistics
AUC _{inf} , AUC _{last} , C _{max}	N, arithmetic mean, median, cv%, standard deviation, minimum, maximum, geometric mean and geometric cv%.
T _{max}	N, median, minimum, maximum.
t _{1/2}	N, arithmetic mean, median, cv%, standard deviation, minimum, maximum.

Table 4. PK Parameters to be Summarized Descriptively by Treatment

Box and whisker plots for individual participant parameters (AUC_{inf}, AUC_{last} and C_{max}) will be presented by treatment and overlaid with geometric means.

Supporting data from the estimation of $t_{1/2}$ and AUC_{inf} will be listed by treatment: terminal phase rate constant (k_{el}); goodness of fit statistic from the log-linear regression (r²); the percent of AUC_{inf} based on extrapolation (AUC_{extrap%}); and the first, last, and number of time points used in the estimation of k_{el}. This data may be included in the clinical study report.

Presentations for prazosin concentrations will include:

- A listing of all concentrations sorted by participant ID, period and nominal time postdose. The concentration listing will also include the actual times. Deviations from the nominal time will be given in a separate listing.
- A summary of concentrations by treatment and nominal time postdose, where the set of statistics will include n, mean, median, standard deviation, coefficient of variation (cv), minimum, maximum and the number of concentrations above the lower limit of quantification.
- Median concentration time plots (on both linear and semi-log scales) against nominal time postdose by treatment (all treatments on the same plot per scale, based on the summary of concentrations by treatment and time postdose).
- Mean concentrations time plots (on both linear and semi-log scales) against nominal time postdose by treatment (all treatments on the same plot per scale, based on the summary of concentrations by treatment and time postdose).
- Individual concentration time plots by treatment (on both linear and semi-log scales) against actual time postdose (there will be separate spaghetti plots for each treatment per scale).
- Individual concentration time plots by participant (on both linear and semi-log scales) against actual time postdose [there will be separate plots for each participant (containing all treatments) per scale].

For summary statistics, median and mean plots by sampling time, the nominal PK sampling time will be used, for individual participant plots by time, the actual PK sampling time will be used.

8.3. Safety Analysis

A set of summary tables split by treatment will be produced to evaluate any potential risk associated with the safety and toleration of administering prazosin.

8.3.1. Treatment and Disposition of Participants

Participant evaluation groups will show treated and not-treated study participant disposition and will show which participants were analyzed for safety (adverse events and laboratory data). Frequency counts will be supplied for participant discontinuation(s) by treatment.

Page 13 of 17	
DELZED CONELDENTIAL	
PFIZER CONFIDENTIAL	

8.3.2. Demographic and Clinical Examination Data

A breakdown of demographic data will be provided for age, race, weight, body mass index, and height. Each will be summarized by sex at birth and 'All Participants' in accordance with the sponsor reporting standards.

8.3.3. Discontinuation(s)

Participant discontinuations and temporary discontinuations due to adverse events will be detailed and summarized by treatment.

Data will be reported in accordance with the sponsor reporting standards.

8.3.4. Adverse Events

Adverse events will be reported in accordance with the Pfizer reporting standards by treatment.

8.3.5. Laboratory Data

Laboratory data will be listed and assessed against the criteria specified in the sponsor reporting standards.

The baseline measurement for a given period is the planned predose measurement at Day -1 of that period.

8.3.6. Vital Signs Data

Vital Signs data will be databased and available upon request.

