#### 9.3.3. Safety analyses

All safety analyses will be performed on the safety population.

The safety data will be described and summarized in accordance with the Sponsor's Data Standards.

AEs, ECGs, BP, pulse rate, and safety laboratory data will be reviewed and summarized on an ongoing basis during the study to evaluate the safety of participants. Any clinical laboratory, ECG, BP, and pulse rate abnormalities of potential clinical concern will be described. Medical history and physical examination and neurological examination information, as applicable, collected during the course of the study will be considered source data and will not be required to be reported, unless otherwise noted. However, any untoward findings identified on physical and/or neurological examinations conducted during the active collection period will be captured as AEs, if those findings meet the definition of an AE. Data collected at screening that are used for inclusion/exclusion criteria, such as laboratory data, ECGs, and vital signs, will be considered source data, and will not be required to be reported, unless otherwise noted. Demographic data collected at screening will be reported.

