8.3.7. ECG Data

ECG data will be databased and available upon request.

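### Must the SAP add an output for ECG, blood pressure and pulse rate abnormalities because Protocol 9.3.3 says they will be described?

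*SAP*

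**What the plan says.** Protocol 9.3.3 (Safety analyses) makes a commitment covering four kinds of data: "Any clinical laboratory, ECG, BP, and pulse rate abnormalities of potential clinical concern will be described". The same section releases some data from reporting unless otherwise noted. One release covers history and examination findings. The other is limited to eligibility data: "Data collected at screening that are used for inclusion/exclusion criteria, such as laboratory data, ECGs, and vital signs, will be considered source data". On-study ECGs and vital signs are not released.

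The SAP treats the four kinds differently:

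- Laboratory (8.3.5): "Laboratory data will be listed and assessed against the criteria specified in the sponsor reporting standards".
- Blood pressure and pulse rate (8.3.6): "Vital Signs data will be databased and available upon request".
- ECG (8.3.7): "ECG data will be databased and available upon request".

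SAP 6.2 names two data types for the standard safety summaries, adverse events and laboratory data, and 8.3.1 repeats the pair. The opening of SAP 8.3 is general ("A set of summary tables split by treatment will be produced") and names no ECG or vital-sign output.

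Protocol Section 9 allows the SAP to modify what the protocol outlines. It asks for a protocol amendment only when a major modification touches the primary endpoint definitions or their analyses.

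**The concern.** One protocol sentence covers laboratory, ECG, blood pressure and pulse rate abnormalities. The SAP specifies an output for the first and none for the other three, and does not say that it departs from the protocol. The entry of none in SAP Section 1 concerns earlier SAP versions, so it does not settle the matter.

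The omission looks awkward for this drug. Prazosin lowers blood pressure both supine and standing (Protocol 2.2.1). Protocol 7.1 makes a significant change in vital signs a reason to stop study intervention, and 8.2.2 defines orthostatic hypotension. Safety and tolerability is the secondary objective. If an abnormal reading met a level of potential concern but the investigator did not call it an adverse event, an analyst following the SAP would produce nothing that shows it.

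**Working it through.** There is no stated figure to reproduce. The check is what the missing output would contain and whether any conclusion depends on it.

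**1. Scheduled readings** (Protocol Table 1 and footnotes; half-life of 2 to 3 hours and peak at 1 to 3 hours from Protocol 2.2.1)

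| Time | Vital signs | ECG | Relation to dose |
|---|---|---|---|
| Screening | yes | yes | before dosing; eligibility data, exempt under 9.3.3 |
| Hour 0, each period | yes | no | predose |
| 24 hours, last period only | yes | yes | post-dose |
| Early termination | yes | yes | no fixed time |

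The hour-0 readings are predose because 8.2.2 puts blood pressure before a coinciding blood draw, and footnote e makes the hour-0 draw predose.

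**2. Distance from the dose, in half-lives** (elapsed time ÷ half-life)

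- 24-hour reading: 24 ÷ 3 = 8, and 24 ÷ 2 = 12. The fraction remaining is 1/2^8 = 1/256 (about 0.4%) down to 1/2^12 = 1/4096 (about 0.02%).
- Hour 0 of Period 2 or 3, after a washout of at least 7 days: 7 × 24 = 168 hours; 168 ÷ 3 = 56, and 168 ÷ 2 = 84.

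No vital signs are scheduled between hour 0 and hour 24, the interval that contains the peak.

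**3. What a by-treatment display could compare**

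The 24-hour reading is taken in the last period only, so each completer contributes one treatment. In Cohort 1 two sequences of 6 end in each treatment (A: 2 and 6; B: 3 and 4; C: 1 and 5), giving 6 + 6 = 12 per treatment. In Cohort 2 it is 18 per treatment. These are between-participant groups, so the display would lose the crossover comparison.

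**4. The route that does report abnormalities**

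Adverse events are the only safety endpoint listed (Protocol Section 3), and Section 4.1 says tolerability and safety are assessed by monitoring them. Appendix 3 makes abnormal safety assessments, with ECG and vital signs among its examples, adverse events when the investigator judges them clinically significant. SAP 8.3.4 reports adverse events by treatment. Appendix 7 sorts ECG findings by whether they may or do qualify as adverse or serious adverse events, and presents the list as alerts.

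**5. What is left over**

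The remainder is on-study readings of potential concern that the investigator does not call adverse events. The documents give no rate, so no count can be offered. Unscheduled readings, which 8.2.2 permits, could fall near the peak. Those prompted by symptoms are also the ones most likely to be recorded as adverse events already.

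**The case for a change.** The strongest case for a change is that the commitment in Protocol 9.3.3 is a sentence of its own, separate from the one on ongoing review, and is not tied to the investigator's adverse event judgement. Appendix 7 says that many ECG findings may qualify as adverse events, so some need not. SAP 8.3.4 and 8.3.5 invoke sponsor reporting standards, while 8.3.6 and 8.3.7 do not, so those standards cannot be assumed to fill the space. Laboratory data, also collected on Day 2 of the last period, are listed. A listing of ECG and vital-sign abnormalities would be cheap.

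The mismatch in wording stands: a reader of 9.3.3 would expect a description, and the SAP does not plan one. Two parts of the argument are weaker.

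- **Oversight.** SAP 6.2, 8.3.1, 8.3.6 and 8.3.7 agree with one another, and the last two give vital signs and ECGs their own headings and a stated disposition. That reads as a choice, and Protocol Section 9 permits it. Neither document requires the SAP to announce a departure of this kind.
- **Form.** Protocol 9.3.3 does not say that the description must be a planned table or listing. A notable value can be described in the study report from the database, which the SAP keeps.

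**Conclusion.** No change to the plan is needed. The protocol and SAP are worded differently on ECG, blood pressure and pulse rate abnormalities, and the difference is real. It alters no result: the bioequivalence intervals do not use these data, the adverse event endpoint is unaffected, and clinically significant findings reach the report as adverse events. A listing of scheduled values would consist mainly of predose readings and readings 8 to 12 half-lives after a dose, with a few from early termination, so it would say little about blood pressure lowering. Aligning the two sentences would be tidy, but it is housekeeping.

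This rests on three assumptions. Investigators apply the adverse event definition in Appendix 3 to ECG and vital-sign findings. The blood pressure effect does not greatly outlast the plasma concentration; the half-life arithmetic concerns concentration only. Whoever writes the report consults the retained data if an abnormality of concern arises. The number of abnormalities outside the adverse event route is unknown.

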8.3.7. ECG Data

ECG data will be databased and available upon request.

8.3.8. Other Safety Data

COVID data will be listed.

8.3.9. Concomitant Treatments

All concomitant medication(s) as well as non-drug treatment(s) will be provided in the listings.

8.3.10. Screening and Other Special Purpose Data

Screening data will available upon request.

Page 14 of 17

Appendix 1. SAS CODE FOR BE ANALYSIS

An example of the PROC MIXED code is provided below:

Cohort 1:

Comparison of Treatment B Prazosin HCl 1 x 2 mg capsule manufactured at the proposed site (Ascoli) and Treatment C Prazosin HCl 2 x 1 mg capsule manufactured at the proposed site (Ascoli) versus Treatment A Prazosin HCl 1 x 2 mg capsule manufactured at the current site (Barceloneta)

proc mixed data=tab.pk;

class seq period trt subject; model l&var=seq period trt/ ddfm=KR; random subject(seq) /subject=subject(seq); lsmeans trt; estimate 'Treatment B vs Treatment A ' trt -1 1 0 /cl alpha=0.1; estimate 'Treatment C vs Treatment A ' trt -1 0 1 /cl alpha=0.1; ods 'Estimates' out=est&var; ods 'lsmeans' out=ls&var; ods 'covparms' out=cov&var; ods 'tests3' out=tst&var;

run;

/* Letter assignments for treatments (trt) within the estimate statement above are as follows;

Treatment A: Prazosin HCl 1 x 2 mg capsule manufactured at the current site (Barceloneta) under fasting conditions (Reference).

Treatment B: Prazosin HCl 1 x 2 mg capsule manufactured at the proposed site (Ascoli) under fasting conditions (Test 1).

Treatment C: Prazosin HCl 2 x 1 mg capsule manufactured at the proposed site (Ascoli) under fasting conditions (Test 2).*/

Page 16 of 17
PFIZER CONFIDENTIAL

Cohort 2:

Comparison of Treatment E Prazosin HCl 1 x 5 mg capsule manufactured at the proposed site (Ascoli) versus Treatment D Prazosin HCl 1 x 5 mg capsule manufactured at the current site (Barceloneta)

proc mixed data=tab.pk;

```
class seq period trt subject;
model l&var=seq period trt/ ddfm=KR;
random subject(seq) /subject=subject(seq);
lsmeans trt;
estimate 'Treatment E vs Treatment D ' trt -1 1 /cl alpha=0.1;
ods 'Estimates' out=est&var;
ods 'lsmeans' out=ls&var;
ods 'covparms' out=cov&var;
ods 'tests3' out=tst&var;
```

run;

/* Letter assignments for treatments (trt) within the estimate statement above are as follows;

Treatment D: Prazosin HCl 1 x 5 mg capsule manufactured at the current site (Barceloneta) under fasting conditions (Reference).

Treatment E: Prazosin HCl 1 x 5 mg capsule manufactured at the proposed site (Ascoli) under fasting conditions (Test).

.*/

Page 17 of 17	
PFIZER CONFIDENTIAL
